**2.2 Study Design**

100 depressed and 50 control subjects, age 18-80, male and female, will be recruited for this study. Depressed participants will be stratified based on their c-reactive protein (CRP) levels (i.e., “High” CRP $\geq$ 3 and “Low” CRP<3). All participants will be started on either 10 mg of escitalopram + placebo or 10 mg of escitalopram + celecoxib (400mg/day) daily for 3 days. Following this lead-in dose of the SSRI they will then take 20 mg daily thereafter for 39 days and have no changes in their dose of placebo or celecoxib. Follow-up visits for all depressed participants will occur at 1 week, 2-weeks, and 4-weeks, following the start of treatment. The study coordinator and PI will monitor side effects and vital signs, and the PI may adjust the medication dosage depending on the patient's response to treatment and/or the presence of side effects. Final dose (10 mg versus 20 mg, or a dose between 10 mg and 20 mg, e.g., 15 mg) will be determined by clinical response and side effects. This decision will be based on an ongoing discussion between the participant and the study doctor. Participants who remit will have their end of study visit with a blood draw, and neuropsych testing at 6 weeks. Participants will then taper off medication at 10 mg for 3 days (if taking 20 mg during study). Based on past studies, less than 10% of participants will be taking less than 20 mg/day of SSRI at the end of the study.

Participants initially randomized to escitalopram + placebo, who do not remit will be treated with 6 weeks of escitalopram + celecoxib. They will not repeat the baseline visit, but will re-complete medication visits at week 1,2, and 4, After the 6 weeks of escitalopram + celecoxib they will undergo a 3rd MRI, neurocognitive session, and blood draw. Those who complete the study at this point will taper off medication at 10 mg for 3 days.

CONFIDENTIAL

Participants will have total study participation of 6-12 weeks. Participants may have unscheduled visits occur throughout the course of the study (screening-completion), if participants are unable to complete the required assessments within the allotted time period. If this occurs participants will be compensated for the travel to these additional visits, but no changes will be made to their human subjects payment. Non-depressed, control group participants will not receive the study drug, and they will not attend the medication check visits at week 1, 2, and 4. Therefore, they will have 3-4 study visits: 1-2 screening visits, 1 baseline visit: blood draw, MRI, and neuropsych testing; Week 6 visit: blood draw, MRI scan, and neuropsych testing.

Participants will be recontacted six months post-study completion to assess efficacy and longevity of the treatment. At the six-month follow-up, participants will be asked to complete a series of questionnaires regarding their medical and psychiatric history. This follow-up appointment is optional.

### **2.3 Study duration**

The study will be ongoing until recruitment is completed. The goal is to complete recruitment in four years. Individuals will participate in the study for approximately 6-12 weeks (from screening through to the last assessment, dependent on whether or not they enter the open-label phase of the study).

### **2.4 Resources necessary for human research protection**

To reduce risks to participants, only physicians and scientists with extensive training and experience will supervise and perform procedures.. Additionally, participants will be provided with phone numbers of research personnel whom the participants may call if they are experiencing any discomfort so that the research personnel can coordinate appropriate response and care. Medication will be packaged by UPenn's Investigational Drug Service (IDS) and will be dispensed to the research team who will pick up the medication on the day it is to be given to the participant. If there is a gap between picking up the medication and dispensing it, the pills will be kept in locked cabinets behind locked doors until the appointment. While taking the medication, participants will be closely monitored for any side effects from taking escitalopram or celecoxib. Several safeguards will be put into place for protecting the confidentiality of research material. Staff members will also be trained to understand the importance of confidentiality. Information gathered about individual participants is maintained in secured storage areas at each site. All phone screenings during the recruitment process will be conducted in a private office area, and after asking the potential participant if they are in an environment where they feel comfortable answering questions related to their eligibility to participate. All aspects of the informed consent process will be conducted in a private consultation room. Study procedures will occur in a private room by personnel trained in following procedures whereby the privacy of the participant is maintained. All psychological assessments will be conducted by experienced and highly trained researchers or clinicians. All assessments will be conducted in

CONFIDENTIAL

private rooms to ensure privacy and the maintenance of confidentiality. Only information necessary for the completion of this study will be collected. All computer data obtained from the laboratory and from research interviews will be identified by a code number. All data will be kept in locked file cabinets and only made available to qualified research personnel. Only code numbers will appear on any data and documents used for evaluation or statistical analysis for this study. Publications emanating from this research will not identify individual patients. HIPAA compliance will be enforced as per University of Pennsylvania policy. Reports from patients' clinical records concerning research observations will not be available to outside medical facilities without the written consent of the participant. It is not anticipated that additional medical or psychological services will be necessary as a consequence of this research; however, should that event occur, participants will be referred to the appropriate service provider and the study coordinator and PI will follow-up to ensure that services were received if necessary.

### **2.5 Target population**

One-hundred depressed subjects, aged 18-80, right handed, male and female (50 with high-CRP levels ( $CRP \geq 3$ ) and 50 with low-CRP levels ( $CRP < 3$ )). In addition, 50 non-depressed controls, matched on demographic and vascular risk factors.

### **2.6 Subjects Enrolled at Penn**

N=150

### **2.7 Accrual**

One hundred depressed participants will be recruited from the community, from outpatient psychiatry clinics at the University of Pennsylvania (General Outpatient Psychiatry, Family Medicine, Geriatric Psychiatry, the Treatment Resistant Depression Clinic, the HUP consult liaison services), and from the Veterans' Administration Medical Center to complete this study with usable data. Fifty non-depressed control participants will also be recruited from the community and the aforementioned sources to complete this study with usable data.

Careful consideration was provided to the determination of sample size requirements. The following section breaks down the statistical methods and theoretical justification for our sample size of 150 participants: 100 depressed (High and Low CRP groups) and 50 control.

Aim 1: Characterize neuroanatomical and neuropsychological effects of abnormal cytokines in MDD. Hypothesis 1a: Inflammatory cytokines will be elevated centrally and peripherally relative to matched controls; neuropsychological performance will be poorer in MDD; hippocampus, amygdala and PFC volumes will be decreased in MDD; and connectivity of hippocampus and amygdala to rostral AC and DLPFC will be decreased in MDD. The power for the IL-6 mean differences was based on our preliminary IL-6 data where the mean (SD) difference is 2.1 (3.6), with 80% power, two-tailed t-test at 5% significance level. A t-test was used to estimate the power to compare the mean difference of regional correlations (functional connectivity) and neuropsychometric function between controls and depressed subjects. To achieve 80% power

CONFIDENTIAL

with a two-tailed test and 5% significance level, an effect size (mean difference/SD) of at least .49 can be detected for a sample of 150 subjects, where 50 are controls. Based on our preliminary data, the group difference of the mean (SD) Fisher-z of the amygdala-subgenual AC is 0.23 (0.17), and of hippocampus-DLPFC is -0.24 (0.12). The preliminary neuropsychometric data supports this power analysis and requires a group difference of the mean (SD) for episodic memory of -1.44 (2.96) and for executive function of -1.64 (3.35).

Hypothesis 1b: Cytokine levels will be correlated with hippocampal and amygdala volumes and PFC thickness; To examine correlational hypothesis 1b, we used a Fisher's r-to-Z transformation test for a correlation between IL-6 and volumetric measures. To achieve 80% power with a two-tailed Z test and 5% significance level, a correlation of |.23| can be detected for a sample of 150 subjects. Based on our preliminary data for IL-6 and for left CA2-3 we have a correlation of .33.

Aim 2: Characterize the effects of treatment on depression and the association with inflammation. Hypothesis 2a: Subjects randomized to treatment will have greater normalization of IL-6 and functional connectivity compared to those randomized initially to placebo. To achieve 80% power with a two-tailed t-test and 5% significance level, a mean difference of 2.1 can be detected with a standard deviation of 3.6 for a sample of 50 medicated and 50 nonmedicated subjects. Based on our preliminary data for IL-6, the mean (SD) difference, between the nonmedicated and medicated group for IL-6 is 2.7 (3.6). We will test Hypothesis 2a for improvement in functional connectivity with repeated measures ANOVA with the treatment group x time interaction result testing whether improvement in the outcome variables (increase in hippocampus and amygdala connectivity to DLPFC and AC) is greater in the treatment group than the placebo group, over and above non-specific changes over time (e.g., practice effects, naturalistic changes) that would be seen also in the control group. Our sample size of 100 with 50 in each group provides 80% power to detect a moderate effect size of .38 with .7 intraclass correlation on the group x time interaction, based on a two-tailed F-test with 5% significance level and assuming 10% attrition.

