### **1.1 *Introduction***

Major depression (MDD) is a cause of disability worldwide, but the etiology of MDD remains unclear. An emerging concept is that inflammation may have relevance, especially in MDD. We have data supporting increased inflammatory cytokines in MDD compared with controls that are associated with decreased hippocampus and amygdala volumes. MDD also had impairment in neuropsychological function in episodic memory, executive function, decreased hippocampus and amygdala resting state functional connectivity. Antidepressant treatment improved IL-6 levels, neuropsychological testing and resting state connectivity.

We will recruit patients with MDD (n = 100) and controls (n = 50) to characterize immune function, brain structure and connectivity and neuropsychological function. Using the Hospital of University of Pennsylvania's Pepper Lab we will measure participants' c-reactive protein (CRP) levels, and stratify participants according to CRP level (i.e. high (CRP  $\geq$ 3) and low (CRP  $<$ 3)). All participants with MDD (n=100), will receive a selective serotonin reuptake inhibitor (SSRI) antidepressant and we will randomize them to SSRI plus placebo (n $\leq$ 50) or SSRI + celecoxib (n $\leq$ 50). We will assess participants pre- and post-treatment with peripheral and central cytokine levels, neuropsychological tests and brain resting state functional connectivity.

Hypothesis 1: a) Compared with matched controls, MDD will have abnormalities in peripheral and inflammatory cytokines, neuropsychological function, hippocampal, amygdala and prefrontal cortex (PFC) structure and functional connectivity; b) Peripheral/central inflammatory cytokine levels will be associated with volume loss in hippocampus and amygdala; and c) Cumulative duration of depression will correlate with volume loss in hippocampus, amygdala, and PFC. d) Across the lifespan there will be an age effect interaction with depression.

Hypothesis 2: a) Once subjects have completed the antidepressant treatment, they will have greater normalization of IL-6 and IL-10, greater improvements in memory, executive function, and in resting state functional connectivity compared to their baseline measures; b) Improvement in clinical depressive scores will correlate with normalization of inflammatory cytokines; c) Those randomized to the addition of celecoxib (vs placebo) will have additive improvements in cytokines, resting state functional connectivity and depression scores.

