### **5    Study Procedures**

#### **5.1    Informed Consent Process / HIPAA Authorization**

100 depressed participants will be recruited from the community, from outpatient psychiatry clinics at the University of Pennsylvania (General Outpatient Psychiatry, Family Medicine, Geriatric Psychiatry, the Treatment Resistant Depression Clinic, the HUP consult liaison services), and from the Veterans' Administration Medical Center. Fifty non-depressed control participants will also be recruited from the community and the aforementioned sources. These participants initially will be contacted by research staff via telephone to conduct a phone screen interview and also to explain the study, including the time commitment required for participation and the basic procedures to be completed. This information is required to determine eligibility and is directly related to our inclusion/exclusion criteria. The information obtained through the phone screen is our way of ruling out specific and obvious things that will determine if a person meets preliminary inclusion/exclusion criteria without having to make a trip to this facility. We are requesting a waiver of documentation of informed consent for this procedure; verbal informed consent will be obtained from all subjects. Individuals who are patients in the Penn system will be asked for verbal consent during the pre-screening to release their PennChart electronic medical record. Data from the PennChart electronic medical record will be viewed only. The information will not be downloaded or stored. Individuals without a PennChart electronic medical record will have one created for them in order to participate in full screening study procedures (i.e. blood draw and EKG). Individuals who are not in the Penn system will be asked to complete a medical record release authorization form at the screening visit after they have signed the informed consent. Upon receipt of their medical records, personal health information and identifiers will be redacted to mitigate the risk of loss of confidentiality and privacy. For those who pass the initial phone screening, an appointment will be scheduled for an in-person visit to complete the informed consent process and to conduct a diagnostic screen, blood draw to determine CRP levels, the presence of HIV, Hepatitis B and C, autoimmune disease, and rheumatoid factor, and EKG to further assess eligibility. There will be time between the phone screen and the in person visit so that participants can consider participation and discuss the study with family and friends. Following the diagnostic assessment and EKG, if a participant continues to be eligible for participation, s/he will receive a second consent that addresses the expectations for participation in the entire study. Additionally, participants will be provided a copy of the consent to keep for their files which will contain all research staffs' contact information. Prior to participation, the research staff will thoroughly review the consent form, answering any and all questions. The participant will be made aware that participation is entirely voluntary and he/she may stop at any time during the study, including after signing the consent form. As mentioned previously, unscheduled visits may occur if assessments required are not completed within the allotted time.

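### Section 2.7 presents 100 depressed participants and 50 controls as completers, but these are also the enrolled and randomised numbers, and the plan's own 10% attrition leaves about 90 depressed completers

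*Combined protocol and SAP*

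**What the plan says.** Section 2.7 (Accrual) frames both accrual targets as people who finish with analysable data. For the depressed group the list of recruitment sources ends with the Veterans' "Administration Medical Center to complete this study with usable data". For controls it reads: "Fifty non-depressed control participants will also be recruited from the community and the aforementioned sources to complete this study with usable data". The same section then justifies "our sample size of 150 participants: 100 depressed (High and Low CRP groups) and 50 control".

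Elsewhere the same numbers carry a different meaning:

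- Section 2.6 gives 150 as the number of subjects enrolled.
- Section 1.1 makes 100 the number randomised: "All participants with MDD (n=100), will receive a selective serotonin reuptake inhibitor (SSRI) antidepressant and we will randomize them to SSRI plus placebo" or to SSRI plus celecoxib, each arm printed as at most 50.
- Section 5.1 repeats the recruitment sentence without the completer wording: "100 depressed participants will be recruited from the community".

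Attrition appears once as a number. The Hypothesis 2a connectivity statement in section 2.7 takes 50 per group and is "based on a two-tailed F-test with 5% significance level and assuming 10% attrition". The Hypothesis 2a IL-6 statement just before it uses 50 against 50, a difference of 2.1, SD 3.6 and 80% power, with no attrition allowance. Section 6.1 expects some participants to be lost to follow-up and plans multiple imputation. The supplied text gives no replacement rule and no enrolment number inflated for dropout.

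**The concern.** A sample size can describe people enrolled or people evaluable. Here 100, 50 and 150 serve as both, and the two agree only if nobody drops out, which the plan does not expect. Someone reading section 2.7 alone would expect 100 depressed participants with week 6 data. Someone reading sections 1.1 and 2.6 would stop at 100 randomised and get fewer.

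At stake is whether the stated power belongs to the trial that will be run. The two Hypothesis 2a calculations concern the same randomised participants at the same follow-up visit, yet one allows for dropout and the other does not.

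**Working it through.** **Inputs.** 100 depressed, 50 controls, 150 in total (sections 2.5 to 2.7); at most 50 per randomised arm (section 1.1); 10% attrition (section 2.7, connectivity statement); IL-6 difference 2.1, SD 3.6, 50 per group, two-sided 5% (section 2.7, Hypothesis 2a). The IL-6 statement calls its groups medicated and nonmedicated, although every depressed participant receives escitalopram. I read them as the two randomised arms.

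**1. Completers expected from the stated enrolment.**
- Depressed: 100 × 0.9 = 90, or 45 per arm.
- Controls: the plan gives no attrition rate. With 0% all 50 complete; if 10% is assumed, 50 × 0.9 = 45.

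**2. Enrolment needed for the stated completers.**
- Depressed: 100 / 0.9 = 111.1, rounded up to 112, or 56 per arm against a limit of 50.
- Controls, under the same 10% assumption: 50 / 0.9 = 55.6, so 56.
- Total on that assumption: 112 + 56 = 168 against 150. With no control attrition: 112 + 50 = 162.

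**3. The plan's IL-6 figure reproduced.** Two-sample t-test with n per arm, noncentrality δ / (σ√(2/n)), 2n − 2 degrees of freedom.
- n = 50: standard error 3.6 × √(2/50) = 0.720; noncentrality 2.1 / 0.720 = 2.917; power 0.82 (0.83 by normal approximation). The difference detectable with 80% power is 2.04.
- Required n by normal approximation: 2 × [(1.960 + 0.842) × 3.6 / 2.1]² = 46.1, so 47 per arm.

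The stated 80% is therefore met, with a little to spare, if all 50 per arm are evaluable.

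**4. The same calculation after 10% attrition.**
- n = 45: standard error 3.6 × √(2/45) = 0.759; noncentrality 2.1 / 0.759 = 2.767; power 0.78 (0.79 by normal approximation). The difference detectable with 80% power is 2.15.
- 45 is below the 47 per arm needed.

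**5. At the preliminary IL-6 difference of 2.7 (SD 3.6) in section 2.7.** Power is 0.96 at 50 per arm and 0.94 at 45.

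**6. Aim 1.** The Hypothesis 1a statement reproduces: 100 against 50 gives a detectable effect of 0.488 SD with 80% power, against the stated 0.49. Sections 6.1 and 6.3 draw the Aim 1 data from baseline, so dropout after baseline costs that aim little.

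**The case against.** The best defence is that the completer wording expresses intent and nothing more. Section 5.1 repeats the sentence without it, and section 2.6 gives an enrolment number, not a worded cap. The 10% is stated for one comparison in the depressed group and sits in section 2.7 itself, so the authors knew of attrition and allowed for it there. The numerical consequence is small: a few points of power at a difference of 2.1, and 0.94 at the preliminary difference. Imputation may also recover some information from people who leave early.

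Most of this stands, and it limits the size of the point. It does not remove the inconsistency. Even as intent, 100 usable completers from 100 randomised conflicts with 10% attrition. The IL-6 comparison uses the same participants at the same week 6 visit as the connectivity comparison, so there is no evident reason to allow for dropout in one and not the other.

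A reader might go further and infer that dropouts will be replaced, that replacements must be steered to the arm with more losses, and that the trial is therefore built around completers. The documents do not support this:

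- They state no replacement rule and no completer quota per arm; section 1.1 gives an upper limit per arm. A completer target could also be reached by giving each added participant the next code in the randomisation sequence.
- Nothing restricts the analysis to completers, and section 6.1 plans imputation for people lost to follow-up.
- Withdrawal under section 10.2 concerns worsening depression or intolerance of escitalopram, which both arms receive. The blood-pressure exclusion in section 10.5.2 is tied to celecoxib, but no dropout figures by arm are given.

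**Conclusion.** The inconsistency is real and its effect is modest. The plan states a completer number that its own enrolment and attrition figures do not deliver: about 90 depressed completers, 45 per arm, instead of 100. For IL-6 under Hypothesis 2a, power at a difference of 2.1 falls from 0.82 to 0.78, and the detectable difference rises from 2.04 to 2.15. The connectivity statement already carries an attrition allowance and is not affected by this point.

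Three assumptions matter. The 10% rate is taken to apply to the IL-6 comparison as it does to connectivity. Participants who are lost are taken to add nothing to the week 6 comparison, which is slightly pessimistic if imputation recovers some information. Any figure for control dropout is my assumption, because the plan gives none. The conclusion does not extend to biased allocation or a completer-only analysis.

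**What to change.** 1. In section 2.7, replace the completer wording with a statement that 100 depressed participants are randomised (50 per arm) and 50 controls are enrolled, with about 90 depressed participants expected to complete at 10% attrition. If an expected number of control completers is wanted, state the rate it assumes.
2. Restate the Hypothesis 2a IL-6 calculation at 45 per arm: about 78% power for a difference of 2.1, or 80% power for 2.15, both with SD 3.6.
3. State in section 6.1 that all randomised participants are analysed in their assigned arm, using the multiple imputation already planned there.

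The cost is a few sentences and no extra participants. The stated completer number and the IL-6 power become slightly less favourable. If the sponsor prefers to keep 100 depressed completers, the limits in sections 1.1 and 2.6 would have to rise to match, by about 12 depressed participants at the plan's own attrition rate.

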## 5.2 Recruitment, screening and baseline assessments

Brief Summary of Procedures (also see attached schedule of procedures and assessments):

Potential participants will be recruited from the community or they may be approached by collaborating clinicians or research team members (see recruitment plans) to explore potential participant's interest in taking part in a research study. Those who are interested will receive a telephone call from research staff to conduct a telephone screen. Those who pass the phone screen will receive an appointment to come to the research location to review and sign the informed consent form for screening purposes and to complete baseline diagnostic assessment screen, blood draw to test for CRP level, Hepatitis B and C, HIV, and rheumatoid arthritis, and will also complete an EKG to determine eligibility. Those who are eligible will return for a baseline visit and will review and sign another informed consent form for participation in the full protocol. Once fully consented, participants will undergo a series of visits to conduct multiple assessments which will include:

- (1) Psychological and Neuropsychological Tests at baseline and week 6; Open Label at week 6;
- (2) Medical Examination;
- (4) 3-4 Blood Collections (blood draw at screening, blood draw at baseline, blood draw at week 2 for liver function and hematocrit assessment, and one at Week 6) for those who enter the open-label phase they will receive an additional 2 blood draws (one at Open Label Week 2 to assess for liver function and hematocrit levels, and one at Open Label Week 6). All participants will be asked if willing to participate in additional blood collection for immune profiling.
- (5) 2-3 MRIs, one at baseline, one at week 6, and one at open-label week 6; the baseline scan will occur before treatment begins;
- (6) 2-3 fMRI (one at baseline which will occur during the same baseline MRI session, one at Week 6, and one at open-label week 6);
- (7) Optional Nutrition Assessment. Participants will be asked to do a 24-hour dietary recall. The food recall will also be collected using the Nutrition Data System for Research (NDSR). Participants are guided through a multiphase interview where they are guided to recall all the food they ate in the preceding 24 hours.

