## **6 Analysis Plan**

### **6.1 Data Analysis and Predictions**

At a basic level, the design of this trial is simple repeated measures design with a) two replicates (time points) b) baseline covariates and outcomes, and c) a single between-person factor (initial case-control depression status). The data collected at two time points to be included in analysis (pre- and post-treatment) will be the depression severity, inflammatory markers, resting state functional connectivity and neuropsychometric data. There have been no published studies to date examining adjuvant celecoxib and SSRI treatment in patients who simultaneously received assessment of inflammatory biomarkers. However, based on our own small pilot sample we will have greater than 85% power to detect differences in changes in IL-6 between SSRI responders and SSRI + celecoxib responders. Volumetric data and confounders to be included in the analysis will be collected at baseline. Classic models of change scores can be used where the baseline level can be controlled giving the so-called residual change score. Use of residualized change scores has several analytic advantages: (1) control for variance (the best predictor of today's value is yesterday's value), (2) statistically each subject is started at the same point. Thus, our estimation model will be extended from the classic model of change scores to a repeated measures ANOVA (analysis of variance) or mixed model repeated measures design. A joint modeling approach with mixed models for repeated measures data can be used to address within-subject variation and between-subject variation of the repeated measurements of multiple

CONFIDENTIAL

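### The 80% power for a .38 group-by-time effect does not follow from its stated inputs, and the Aim 2 IL-6 power statements describe comparisons other than the randomised one

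*Combined protocol and SAP*

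**What the plan says.** **Connectivity, group by time.** Section 2.7 (Aim 2, Hypothesis 2a) says that 100 depressed participants, divided equally between two arms, "provides 80% power to detect a moderate effect size of .38 with .7 intraclass correlation on the group x time interaction". The same sentence describes the calculation as "based on a two-tailed F-test with 5% significance level and assuming 10% attrition". It does not say what .38 is a multiple of. The only effect-size definition in Section 2.7 is under Aim 1, for the comparison of depressed participants with controls: "an effect size (mean difference/SD) of at least .49 can be detected for a sample of 150 subjects, where 50 are controls". Section 6.1 describes the design as having "two replicates (time points"), before and after treatment. Section 5.2 lists "2-3 MRIs, one at baseline, one at week 6, and one at open-label week 6", so the third scan belongs to the open-label phase. Section 2.7 also recruits its 100 depressed participants "to complete this study with usable data", which reads as completers, while the power sentence allows for attrition.

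**IL-6 under Aim 2.** There are three power statements:
- Section 2.7 gives 80% power for a difference of 2.1 with SD 3.6 "for a sample of 50 medicated and 50 nonmedicated subjects". It cites a preliminary nonmedicated-versus-medicated difference of 2.7 (3.6).
- Section 6.1 gives more than 85% power for the change in IL-6 between SSRI responders and SSRI plus celecoxib responders.
- Section 6.1 gives more than 95% power from randomising about 53 subjects in a Phase II.

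**The design.** Under Sections 1.1, 2.2 and 4.2, every depressed participant takes escitalopram and is randomised once to add celecoxib or placebo. Under Sections 2.2 and 5.2, placebo-arm non-remitters then go to open-label escitalopram plus celecoxib. The title calls the trial one-phase.

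**The concern.** Hypothesis 2c (Section 1.1) rests on celecoxib versus placebo for cytokines and connectivity, and Section 2.1 lists IL-6 and resting-state connectivity among the primary outcomes. The power statements should tell a reader what effect this comparison could detect.

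For connectivity they do not. If .38 is mean difference/SD, a null result would look better powered than it was. If .38 is Cohen's f, the trial is better powered than stated.

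For IL-6 the statements answer other questions. A pilot difference between medicated and nonmedicated people does not show what adding celecoxib to escitalopram could produce. Responders are a group defined after randomisation. The current design describes no randomisation of 53 subjects.

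**Working it through.** **Method check on neighbouring figures (Section 2.7).**
- Effect .49 with 100 versus 50: noncentrality = .49 × √(100 × 50/150) = 2.83, 148 df, power 80.3%. The stated 80% is reproduced.
- Correlation .23 with n = 150: atanh(.23) × √147 = 2.84, and Φ(2.84 − 1.96) = 81.0%. Also reproduced.

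**Inputs for the group-by-time claim.** 50 per arm, ICC .7, two-tailed 5% and 10% attrition, hence 45 per arm (Section 2.7); two time points (Section 6.1).

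**Formula.** With two time points, the interaction F-test is the two-sample t-test on change scores. With δ the effect and n per arm, noncentrality = (δ/SD of change) × √(n/2), on 2n − 2 df.

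*.38 as mean difference/SD.*
- SD of change = √(2 × (1 − .7)) = .775, so .38/.775 = .491.
- 45 per arm: .491 × √22.5 = 2.33, critical t 1.987, power 63.4%.
- 50 per arm: .491 × √25 = 2.45, critical t 1.984, power 68.0%.

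*The same, baseline-adjusted.* Residual SD = √(1 − .7²) = .714, so .38/.714 = .532. Power is 70.4% and 75.0%.

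*.38 in change-score SDs.* Noncentrality is 1.80 and 1.90. Power is 43.0% and 46.9%.

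*.38 as Cohen's f.* λ = f²N = .1444 × 90 = 13.0 and .1444 × 100 = 14.4, giving 94.6% and 96.4%. With λ = f²(N − 2) it is 94.1% and 96.1%. If λ is also divided by (1 − ICC), power exceeds 99.9%.

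| Scale of .38 | Power, 45 / 50 per arm | Detectable at 80% power, 45 / 50 |
|---|---|---|
| Mean difference/SD, change score | 63% / 68% | .46 / .44 SD |
| Mean difference/SD, baseline-adjusted | 70% / 75% | .43 / .40 SD |
| Change-score SD | 43% / 47% | .60 / .57 |
| Cohen's f (λ = f²N, no gain from the ICC) | 95% / 96% | f = .30 / .28 |

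**Routes that do reach 80%.** Each contradicts the text.
- Baseline against the mean of two later scans: variance of the contrast = .3 × 1.5 = .45, power 75.7% at 45 and 80.1% at 50. The randomised phase has one later scan, and 50 per arm ignores the attrition.
- 100 versus 50 without attrition: power 80.3% (76.0% at 90 versus 45). The sentence says 50 in each group.
- One-sided, baseline-adjusted test at 45 per arm: 80.5%. The sentence says two-tailed.

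**IL-6, arithmetic.** 2.1/3.6 = .583. Power is 82.3% at 50 per arm and 78.1% at 45, so the stated 80% is adequate at the stated size.

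**IL-6, contrast.**
- *Medicated versus nonmedicated (2.7).* All 100 depressed participants receive an SSRI, so there is no nonmedicated depressed arm.
- *Responders (6.1).* This subset is selected after randomisation, not the randomised arms.
- *53 subjects in Phase II (6.1).* The SSRI plus celecoxib versus SSRI plus placebo contrast is the right one, but no second randomisation is described. At most the 50 placebo-arm participants could enter the open-label phase, fewer than 53.

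**IL-6, what 3.6 would support.** The documents do not say whether 3.6 is an SD of change.
- If it is, the difference detectable at 80% power is 2.15 units at 45 per arm and 2.04 at 50.
- If it is a single-time SD, SD of change = 3.6 × √(2(1 − r)). With an assumed r of .3 to .7 this is 4.26 to 2.79. The detectable difference is then 2.54 to 1.67 at 45 per arm, or 2.41 to 1.58 at 50.

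**The case against.** The strongest reply is that underpowering has not been shown. The plan never defines .38, the mean difference/SD reading is borrowed from a different test, and under Cohen's f the 80% is an understatement. That stands as a limit on the conclusion: what is established is that 80% does not follow, not that the trial is underpowered.

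Second, Section 6.1 speaks of controlling for baseline, so 70–75% has as good a claim as 63–68%. That is fair. On this scale the range is 63–75%, still short of 80%.

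Third, the 100-versus-50 split gives almost exactly 80%, and Section 6.1 names case-control status as the between-person factor. The figure may have been computed for that contrast. This may explain where it came from, but it does not rescue a sentence about two arms of 50.

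Fourth, the IL-6 problem is one of mismatched text rather than arithmetic, and the 10% attrition is attached only to the group-by-time sentence. Both are true. The 78% is a sensitivity figure, and the objection to that statement is its comparison.

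Last, the remedy changes no analysis or sample size. That makes it cheap, but these sentences are the plan's power justification for two primary outcomes.

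**Conclusion.** The concern holds. With two time points, ICC .7 and a two-tailed 5% test, an effect of .38 gives 63% power at 45 per arm and 68% at 50 if it is mean difference/SD (70% and 75% baseline-adjusted). It gives 43% and 47% in change-score SDs, and at least 94% and 96% as Cohen's f. The stated 80% matches none of these, and whether it is too high or too low cannot be settled until the scale is stated.

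None of the three Aim 2 IL-6 statements supports the power of the randomised celecoxib-versus-placebo comparison. The figures above 85% and 95% cannot be carried over to it, and their size cannot be checked because the documents do not give the estimates behind them. The IL-6 detectable differences shown here depend on treating 3.6 as an SD of change, or on an assumed pre-post correlation.

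The case-control IL-6 statement under Hypothesis 1a, where "the mean (SD) difference is 2.1 (3.6), with 80% power", is not affected.

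**What to change.** In Section 2.7:
- State the scale of .38, and whether 100 means enrolled or completing participants.
- Restate the group-by-time power, or the detectable effect, for escitalopram plus celecoxib versus escitalopram plus placebo. On the mean difference/SD scale, 80% power is for .46 SD at 45 per arm or .44 SD at 50 (.43 or .40 if baseline-adjusted).
- Replace the medicated/nonmedicated IL-6 justification with power for the randomised contrast, using a stated SD of change. If 3.6 is kept, label the resulting figures (2.15 units at 45 per arm, 2.04 at 50) as an assumption, since 3.6 comes from another contrast.
- Leave the Hypothesis 1a IL-6 statement as it is.

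In Section 6.1, remove the responders sentence and the 53-subject randomisation sentence.

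The cost is protocol and SAP wording. The stated power may become less favourable, depending on the scale of .38. No extra patients, visits or analyses are needed.
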